## 3.2. Study Stopping Rules

If the following are observed, the study will be temporarily halted (screening, randomization, dosing of study drug) by the sponsor:

- Two similar (by preferred term [PT]) treatment-related Grade 3 SAEs that are not generally reported in the preterm population; or
- One treatment-related Grade 4 SAE that is not generally reported in the preterm population.

In order to assess whether these SAEs are in the treatment arms, only unblinded study members and/or the IDMC will make the assessment for the need to halt the study. The sponsor will follow the relevant regulatory requirements for reporting of SAEs to regulatory authorities and ethics committees and the data will be submitted to the appropriate authorities as required. A full evaluation will be conducted to determine if it is appropriate to continue the study. In the event the study will be restarted, local regulatory procedures will apply.

Generally reported AEs in the preterm population include but are not limited to: hypothermia, hypoglycemia, respiratory distress, apnea (with or without bradycardia), hyperbilirubinemia, feeding difficulties, poor weight gain, dehydration, respiratory disorders (including bronchiolitis), gastrointestinal disorders, and sudden infant death syndrome.

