#### 7.2.2. Serious Adverse Events

All SAEs, regardless of assessment of causal relationship to study drug must be reported to the sponsor (designee) within 24 hours. Refer to the study manual for the procedure to be followed.

Information not available at the time of the initial report must be documented in a follow-up report. Substantiating data such as relevant hospital or medical records and diagnostic test reports may also be requested.

The investigator must promptly report to the Institutional Review Board/Ethics Review Committee (IRB/ERC) all unanticipated problems involving risks to subjects. This includes death from any cause and all SAEs related to the use of the study drug. It is recommended that all SAEs be reported to the IRB/ERC, regardless of assessed causality.

In the event the investigator is informed of an SAE after the subject completes the study, the following will apply:

- SAE with an onset within 30 days of the end of study/early termination visit the SAE will be reported to the sponsor. The investigator should make every effort to obtain follow-up information on the outcome until the event is considered chronic and/or stable.
- SAE with an onset day greater than 30 days from the end of study/early termination visit only fatal SAEs and those deemed by the investigator to be drug-related SAEs will be reported to the sponsor. The investigator will make every effort to obtain follow-up information on the outcome of a drug-related SAE until the event is considered chronic and/or stable.

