# 7.3. Evaluation of Severity and Causality

## 7.3.1. Evaluation of Severity

The severity of the AE will be graded using 1 of 2 severity scales, and the severity scale used will be determined by the type of AE experienced by the subject.

The severity of AEs related to allergic or anaphylactic reactions (including AESIs) will be graded according to the CTCAE Version 4.0 criteria for grading allergic reactions and anaphylaxis (Appendix D).

The severity of AEs related to other events (excluding allergic or anaphylactic reactions) will be graded according to the Modified Toxicity Grading Scale from Division of AIDS for Grading the Severity of Adult and Pediatric Adverse Events. Two versions are in use for this protocol: Version 1.0, December, 2004; Clarification August 2009 (Appendix E) and Version 2.0, November 2014 (Appendix F, only applicable pages are included).

Notes: Version 2.0 is to be used for grading AEs associated with total bilirubin and hemoglobin. For all other AEs (excluding allergic or anaphylactic reactions) Version 1.0 with the August 2009 clarification should be used.

- 1. For AEs not identified elsewhere in Appendix E, the AE should be graded using the row describing Estimating Severity Grade.
- 2. For AEs associated with abnormal glucose and calcium values, a footnote is present in Version 1.0 of the Division of AIDS (DAIDS) scale indicating that the values are associated with full-term infants. This footnote has been removed from Version 2.0 of the DAIDS scale with no resultant changes to the grading cut-off values. Therefore, for the purposes of this protocol, the values present in Version 1.0 of the DAIDS scale are appropriate to use.
- 3. Any occurrence of fever must be graded according to the scale provided in Version 1.0 of the DAIDS scale. The DAIDS scale specifies a non-axillary temperature range in degrees Celsius. Please refer to Table 6 below for temperature conversion to degrees Fahrenheit and for a breakdown by age of infant.

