# APPENDIX D. TOXICITY GRADING SCALE FOR GRADING ALLERGIC REACTIONS AND ANAPHYLAXIS - COMMON TERMINOLOGY CRITERIAL FOR ADVERSE EVENTS (CTCAE; VERSION 4.0, PUBLISHED 28 MAY 2009; V4.03, 14 JUNE 2010)

The CTCAE descriptive terminology will be utilized for reporting AEs of allergic reactions and anaphylaxis. A grading (severity) scale is provided for each AE term.

Adverse Event	Grade 1	Grade 2	Grade 3	Grade 4	Grade 5
Allergic reaction	Transient flushing or rash, drug fever <38 degrees C (<100.4 degrees F); intervention not indicated	Intervention or infusion interruption indicated; responds promptly to symptomatic treatment (e.g., antihistamines, NSAIDS, narcotics); prophylactic medications indicated for ≤24 hours	Prolonged (e.g., not rapidly responsive to symptomatic medication and/or brief interruption of infusion); recurrence of symptoms following initial improvement; hospitalization indicated for clinical sequelae (e.g., renal impairment, pulmonary infiltrates)	Life- threatening consequences; urgent intervention indicated	Death
Anaphylaxis	_		Symptomatic bronchospasm, with or without urticaria; parenteral intervention indicated; allergy-related edema/angioedema; hypotension	Life- threatening consequences; urgent intervention indicated	Death

Definition: A disorder characterized by an acute inflammatory reaction resulting from the release of histamine and histamine-like substances from mast cells, causing a hypersensitivity immune response. Clinically, it presents with breathing difficulty, dizziness, hypotension, cyanosis and loss of consciousness and may lead to death.

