5.8.1. Adverse Events

The verbatim text, the PT, and the primary SOC will be listed in subject listings. Summaries that include frequencies and proportions of subjects reporting AEs will include the PTs and the SOCs as appropriate.

The focus of adverse event reporting in the clinical study report will be on TEAEs. Pre-treatment and post-treatment AEs will be provided separately.

If an AE date/time of onset (occurrence, worsening, or becoming serious) is incomplete, an imputation algorithm will be used to classify the AE as pre-treatment, treatment-emergent, or post-treatment. The algorithm for imputing date/time of onset will be conservative and will classify an AE as treatment-emergent unless there is definitive information to determine pre-treatment status. For details on handling missing data and partial dates, see Section 6.3.

Summaries of all TEAEs in each treatment group will include:

- Overview of TEAEs, summarizing number and percentage of subjects with any
 - TEAEs.
 - Serious TEAEs.
 - TEAEs leading to death.
 - TEAEs leading to permanent treatment discontinuation.
 - TEAEs with severity of 3/4/5/Severe/Life-Threatening/Fatal (if multiple occurrences of an event for a subject, then worst severity is counted).
 - TEAEs that occurred within 2 days after either the first dose or the second dose (ie, post dose TEAE start date - dosing date \leq 2).
- All TEAEs by SOC and PT.
- All TEAEs by SOC, PT, and severity.
- All TEAEs by SOC, PT, and relationship (related, not related) to study drug.
- All TEAEs by SOC, PT, and relationship (related, not related) to injection procedure.
- TEAEs reported by \geq 5% of subjects in any treatment group by PT ordered by decreasing subject frequency in the combined REGN2222 group.
- TEAEs reported by \geq 1% of subjects in any treatment group by PT ordered by decreasing subject frequency in the combined REGN2222 group.
- Study drug-related TEAEs by SOC and PT.
- Study drug-related TEAEs by SOC, PT, and severity.
- Injection procedure-related TEAEs by SOC and PT.
- Injection procedure-related TEAEs by SOC, PT, and severity.

- Serious adverse events: All, study drug-related, and injection procedure-related TEAEs by SOC and PT.
- Death: All, study drug-related, and injection procedure-related TEAEs by SOC and PT. TEAEs leading to death are TEAEs that led to death regardless of timing of death in relation to study drug injection (ie, death occurring in the TEAE period or during the post-treatment period)

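### The study-halt triggers in Protocol Section 3.2 end at Grade 4, so a fatal (CTCAE Grade 5) treatment-related anaphylaxis is not a listed trigger although a survived Grade 4 one is

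*Protocol*

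**What the plan says.** Protocol Section 3.2 states that, if listed events are observed, "the study will be temporarily halted (screening, randomization, dosing of study drug) by the sponsor". The list has two entries. The first is a pair of treatment-related Grade 3 SAEs sharing a preferred term. The second is "One treatment-related Grade 4 SAE that is not generally reported in the preterm population". The first entry carries the same exemption for events commonly seen in preterm infants. The section adds that "only unblinded study members and/or the IDMC will make the assessment for the need to halt the study".

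Section 3.2 names no grading scale; Section 7.3.1 supplies two. For the reactions at issue here, "The severity of AEs related to allergic or anaphylactic reactions (including AESIs) will be graded according to the CTCAE Version 4.0 criteria", reproduced as Appendix D. That table has five grades for both allergic reaction and anaphylaxis: Grade 4 is life-threatening and Grade 5 is death. Other adverse events go to the DAIDS tables in Appendices E and F, which end at Grade 4.

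The SAP also treats fatal outcomes as a category of their own. Section 5.8.1 tabulates "TEAEs with severity of 3/4/5/Severe/Life-Threatening/Fatal" and has a separate table: "Death: All, study drug-related, and injection procedure-related TEAEs by SOC and PT".

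**The concern.** The two triggers name exact grades. On the scale that the protocol requires for anaphylaxis, death is not part of Grade 4; it has its own grade, which the halt rule does not mention. The rule therefore covers an infant who survives a life-threatening related reaction and omits one who dies of it.

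Hypersensitivity within 48 hours of dosing is the study's designated adverse event of special interest (Section 7.2.4.2), so the omission falls on the worst form of an event the protocol singles out. At stake is whether screening, randomization and dosing stop under the written rule after a related death, or only because someone uses a discretionary power. The efficacy inference is untouched.

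**Working it through.** The plan states no figure to reproduce. The check sets the passages side by side and then applies the rule to every case.

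**Inputs**

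- Trigger 1 (Protocol 3.2): two similar treatment-related SAEs of Grade 3.
- Trigger 2 (Protocol 3.2): one treatment-related SAE of Grade 4.
- Scale for anaphylaxis (Protocol 7.3.1 and 7.2.4.2): CTCAE, Appendix D, Grades 1 to 5. The definition printed there recognises that the reaction can involve "cyanosis and loss of consciousness and may lead to death". It is the separate Grade 5 column, not this definition, that shows death is graded apart from Grade 4.
- SAE status (Protocol 7.1.2): every death is an SAE. A fatal related anaphylaxis therefore satisfies the SAE and relatedness conditions and fails on the grade alone.
- Exemption (Protocol 3.2): the examples of events common in preterm infants do not include anaphylaxis, although the list is open-ended.

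**Wording elsewhere.** The rule for stopping an individual infant's dosing (5.2.2.1) applies from Grade 3 upward. The rule for reporting laboratory abnormalities as adverse events (7.2.6) does too. Open-ended grade wording was in use in this protocol; the study-level rule lacks it.

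**Enumeration.** Take one or two similar treatment-related Appendix D SAEs, each of Grade 3, 4 or 5 and not exempt. There are 3 single events and 6 unordered pairs, so 3 + 6 = 9 sets. Let n3 and n4 be the numbers of Grade 3 and Grade 4 events.

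- As written: a trigger is met if n3 ≥ 2 or n4 ≥ 1.
- Trigger 2 reworded: a trigger is met if n3 ≥ 2 or any event is Grade 4 or higher.
- Both reworded: a trigger is met if at least two events are Grade 3 or higher, or any event is Grade 4 or higher.

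| Set of grades | As written | Trigger 2 reworded | Both reworded |
|---|---|---|---|
| {3} | no | no | no |
| {4} | yes | yes | yes |
| {5} | **no** | yes | yes |
| {3,3} | yes | yes | yes |
| {3,4} | yes | yes | yes |
| {3,5} | **no** | yes | yes |
| {4,4} | yes | yes | yes |
| {4,5} | yes | yes | yes |
| {5,5} | **no** | yes | yes |
| Total meeting a trigger | 5 of 9 | 8 of 9 | 8 of 9 |

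The {3} row is meant to be a no. The other three misses have one cause: Grade 5 is not listed. Rewording trigger 2 removes all three, and rewording trigger 1 as well changes nothing further. The counts show the logic of the rule and are not probabilities; the documents give no rate of fatal reactions.

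**Other provisions that might close the gap.** Section 7.2.2 requires SAEs to reach the sponsor within 24 hours and requires prompt notice to the ethics board of unanticipated problems; "This includes death from any cause and all SAEs related to the use of the study drug". Section 7.2.3 covers expedited reporting, Section 3.3.1 IDMC recommendations, and Section 15.1 the sponsor's right to terminate. Each is a reporting duty or a discretionary power. None requires screening, randomization and dosing to stop after a related death.

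**The case against.** The strongest reply is that nobody would read the rule this way. A fatal anaphylaxis would ordinarily pass through a life-threatening state, Section 3.2 does not say that only the final grade counts, and Grade 4 is naturally understood as a floor. For most adverse events Grade 4 is the top of the scale, so the gap appears only where the CTCAE exception meets a literal reading. The halt is also not automatic, because Section 3.2 leaves the assessment to unblinded members or the IDMC. A related death would reach the sponsor within 24 hours in any case, and the IDMC charter may already deal with it.

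Much of this stands. The floor reading is probably what was intended, the scope is limited to Appendix D events, and in practice the sponsor or the IDMC would very likely act. The SAP severity label is a tabulation category and does not interpret a stopping rule. But the floor reading is not written down, Appendix D separates the two grades, and the listed triggers define which events the rule covers. A safety threshold should not have to be rescued by assumed intent.

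A further objection is that mentioning deaths could blur the exemption, since sudden infant death syndrome is among the exempt examples. If the exemption continues to qualify the whole bullet, that position is unchanged.

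**Conclusion.** The concern holds, as a minor drafting fault. As written, a fatal treatment-related anaphylaxis meets neither trigger in Section 3.2, while a survived life-threatening one does. This rests on a literal reading, on the event being graded on Appendix D as Section 7.3.1 requires, and on anaphylaxis not being treated as a commonly reported preterm event. It does not extend to events graded on DAIDS, whose tables end at Grade 4; the protocol does not say how a fatal event is graded there. The charter could not be checked. No probability is claimed. What is missing is the mandatory wording, not all protection.

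**What to change.** In the second bullet of Section 3.2, replace Grade 4 with Grade 4 or higher and add in parentheses that this includes any treatment-related death. Keep the exemption for commonly reported preterm events as the qualifier of the whole bullet, and leave the first bullet alone. Check the IDMC charter and align it if it does not already cover treatment-related deaths.

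The cost is a few words in one bullet and a charter check. The only downside is a rare additional temporary halt and review after a related death, which is what the rule ought to produce.

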## 3.2.1. End of Study Definition

The end of study will be approximately 180 days after the last dose or approximately 237 days after the first dose, whichever is longer.

## 3.3. Study Committees

#### 3.3.1. Independent Data Monitoring Committee

An IDMC, composed of members who are independent from the sponsor and the investigators, will monitor subject safety by conducting formal reviews of accumulated safety data that will be blinded by treatment group; if requested, the IDMC may have access to the treatment allocation code or any other requested data for the purposes of a risk-benefit assessment.

The IDMC will provide the sponsor with appropriate recommendations on the conduct of the clinical study to ensure the protection and safety of the subjects enrolled in the study. The IDMC will also recommend any measures that may be required for ensuring the integrity of the study results during the study execution.

All activities and responsibilities of the IDMC are described in the IDMC charter.

## 3.3.2. Safety Monitoring Team

A cross-functional safety monitoring team (SMT) at Regeneron Pharmaceuticals, Inc. (Regeneron) will meet periodically to review blinded safety data. These data will include, but may not be limited to:

• TEAEs that result in an early study withdrawal

- SAEs
- Selected laboratory test results
- Additional AEs of interest, as determined by the SMT

Any signals identified through this review will be investigated and monitored. The SMT will propose risk management/mitigation activities as needed and will monitor their impact.

## 3.3.3. Endpoint Adjudication Committee

An adjudication committee will be formed before database lock, to address any categorization of a medically attended respiratory illness event as an endpoint that is unclear. Source documentation will be provided to a blinded adjudication committee for categorization. In addition, any subject deaths occurring after the administration of the first dose of study drug and prior to Day 150 will be assessed to determine their association with RSV.

# 4. SELECTION, WITHDRAWAL, AND REPLACEMENT OF SUBJECTS

## 4.1. Number of Subjects Planned

A total of 1539 subjects are planned to be enrolled, as follows:

- Part A: Single cohort study with approximately 24 subjects planned to receive REGN2222
- Part B: 3-arm study with approximately 505 subjects planned in each of the 3 treatment arms for a total of 1515 subjects (1010 to receive REGN2222 [505 subjects in each of the 2 REGN2222 arms]; 505 to receive placebo)

This study will be conducted at multiple sites in the US, Canada, Australia, and New Zealand, as well as several countries in Europe. Additional countries/regions may be added.

The study population will consist of healthy male and female infants who have a chronological age of  $\leq$ 6 months at the time of first dose (ie, dosing on or before the subject's 6-month birthday), who have a GA no more than 35 weeks, 6 days, and who are not eligible, recommended, nor have access to receive palivizumab by standard practice, local guidelines, or their healthcare provider.

#### 4.1.1. Inclusion Criteria

A subject must meet the following criteria to be eligible for inclusion in the study:

- 1. Preterm, otherwise healthy male or female infant who has a chronological age of ≤6 months of age at the time of the first dose (ie, infant must receive the first dose on or before the subject's 6-month birthday)
- 2. Gestational age at birth is no more than 35 weeks, 6 days
- 3. Parent(s) or legal guardian(s) of the infant is able to understand the study requirements, willing to provide informed consent, and legally able to provide informed consent.

## 4.1.2. Exclusion Criteria

#### 4.1.2.1. Exclusion Criteria for the Infant

An infant who meets any of the following criteria will be excluded from the study:

- 1. Eligible, recommended, and have access to receive palivizumab per AAP or other local guidelines, standard practice, or by their healthcare provider
- 2. Diagnosis of CLD defined as requirement of supplemental oxygen for at least 28 days (cumulative) after birth; exceptions are infants who have received supplemental oxygen as standard of care for reasons other than CLD.
- 3. Known hemodynamically significant congenital heart disease
- 4. Known immunodeficiency, neuromuscular disease, or congenital abnormalities of the airway
- 5. Known renal or hepatic dysfunction
- 6. Serum creatinine, bilirubin, alkaline phosphatase hepatic enzymes (aspartate aminotransferase [AST] and alanine aminotransferase [ALT]) total that is >1.1 times the upper limit of normal for gestational age and chronological age (Appendix G). Exceptions are if the investigator has evidence that increased alkaline phosphatase corresponds to normal bone growth of preterm infancy, if the investigator has evidence that increased indirect bilirubin corresponds to a Gilbert's-type syndrome, or that it corresponds to an increase in bilirubin due to physiological jaundice, breastfeeding jaundice, or other conditions commonly found in otherwise healthy preterm infants and neonates).
- 7. Any other laboratory findings showing evidence of organ dysfunction or any clinically significant deviation from the normal range for gestational age and chronological age, as decided by the investigator at the screening visit
- 8. Use of any concomitant medications within 30 days of the screening visit, including prescription medications (exceptions are those used as standard of care, such as antibiotics, topical analgesic for blood draws [not to be used for IM injections, including vaccines], nutritional supplements, medications for gastroesophageal reflux, topical medications, and eye drops), and over-the-counter medications (except for vitamin supplements, ibuprofen, acetaminophen, or topical creams)
- 9. Vaccine or other IM drug administration within 2 days before or after dosing of the study drug
- 10. History of hospitalization prior to screening; exceptions include hospitalization for delivery and the subsequent stay for preterm infants; uncomplicated or elective surgeries (eg, circumcision, repairs of uncomplicated hernia without sequelae).
- 11. Life expectancy of <6 months
- 12. Major congenital malformations, including congenital cleft palate, cytogenetic abnormalities, or serious chronic disorders
- 13. Known or suspected impairment of immunological functions or autoimmune diseases

- 14. History of anaphylaxis
- 15. History of a seizure disorder
- 16. Previously received palivizumab, IV gamma globulin, or any other investigational RSV prophylaxis or vaccine product
- 17. Previous allergic reaction to IV immunoglobulin, blood products or other foreign proteins, such as vaccines and monoclonal antibodies, or any of the components of the investigational product formulation
- 18. Participation in any clinical research study evaluating another investigational drug or therapy that is inconsistent with current standard of care within at least 5 half-lives of the investigational drug prior to the screening visit

#### 4.1.2.2. Exclusion Criteria for the Mother

An infant will be excluded from the study if the biological mother meets any of the following criteria:

- 1. Is younger than 16 years old or is unable to legally provide informed consent at the time of screening of the infant
- 2. Has self-reported history of illicit drug or alcohol abuse during pregnancy with the infant
- 3. Has self-reported or confirmed history of human immunodeficiency virus or hepatitis B
- 4. Has self-reported history of receiving an investigational RSV vaccine

